4.2.4 Other efficacy outcome endpoints

4.2.4.1 Time to first subsequent therapy or death (TFST)

The time to the start of subsequent therapy will be analysed using the same methodology and model as that used for the primary analysis of PFS. The HR for the treatment effect together with its 95% CI will be presented. In addition, medians and a Kaplan-Meier plot of the time to the start of subsequent therapy will be presented by treatment arm and the time between progression and starting subsequent therapy will be assessed based upon the investigator data defined date of progression. This will be summarised per treatment arm but no formal comparisons will be made. No multiplicity adjustment will be applied as this is viewed as a supportive endpoint.

In patients who received a subsequent anti-cancer therapy, a summary table of first subsequent anti-cancer therapies by treatment arm will be provided.

This analysis will be repeated on the ITT set.

4.2.4.2 Time to second subsequent therapy or death (TSST)

The time to second subsequent therapy will be analysed using similar methodology to that of TFST. This analysis will be repeated on the ITT set.

4.2.5 Safety data

Safety is a secondary objective. Safety and tolerability data will be presented by treatment arm using the safety population. Safety summaries will be descriptive only. No formal statistical analyses will be performed on the safety variables.

The following sections describe the planned safety summaries for AEs, vital signs, laboratory parameters, ECG and World Health Organisation (WHO)/ Eastern Cooperative Oncology Group (ECOG) performance status. However, additional safety summaries (not specified in

this statistical analysis plan [SAP]) may need to be produced to aid interpretation of the safety data.

4.2.5.1 Adverse events

All AEs, both in terms of current MedDRA PT and CTCAE grade, will be summarised descriptively by count (n) and percentage (%) for each treatment group. Any AE occurring before randomised treatment (i.e. before the administration of the first infusion on Study Day 1) will be included in the AE listings, but will not be included in the summary tables (unless otherwise stated). These will be referred to as 'pre-treatment'. However, any AE occurring before the administration of the first dose on Study Day 1 that increases in severity after the first dose will be regarded as treatment emergent and thus will be included in the majority of summary tables.

A treatment emergent AE (TEAE) is an AE with an onset date (and time, if applicable) following the first dose of study treatment, or a pre-existing AE which worsens following the first dose of study treatment through to 90 days after the last dose of study treatment (i.e., the last dose of durvalumab/placebo).

AEs observed up until 90 days following discontinuation of the study treatment (i.e., the last dose of randomised treatment) or until the initiation of the first subsequent anti-cancer therapy (excluding palliative radiotherapy) following discontinuation of study treatment (whichever occurs first) will be used for reporting of all the AE summary tables. For all IDMC and interim analyses (IAs) deliveries, this will take into account the earliest date from: AEs observed up until 90 days following discontinuation of the study treatment, initiation date of the first subsequent anti-cancer therapy (excluding palliative radiotherapy) or the data cut-off (DCO) date applicable to that delivery.

This will more accurately depict AEs attributable to study treatment only as some of AEs up to 90 days following discontinuation of the study treatment are likely to be attributable to subsequent therapy.

However, to assess the longer-term toxicity profile, some of the AE summaries will also be produced containing AEs observed up until 90 days following discontinuation of the study treatment (i.e. without taking subsequent therapy into account)

Any events in this period that occur after a patient has received further therapy for cancer (following discontinuation of study treatment) will be flagged in the data listings.

All reported AEs will be listed along with the date of onset, date of resolution (if AE is resolved) and investigator's assessment of severity and relationship to durvalumab/placebo/

CRT. Frequencies and percentages of patients reporting each PT will be presented (i.e. multiple events per patient will not be accounted).

AEs that have missing causality (after data querying) will be assumed to be related to study drug.

A separate data listing of AEs occurring more than 90 days after discontinuation of IP will be produced. These events will not be included in AE summaries, unless otherwise stated.

Any AE occurring before treatment with IP will be included in the data listings but will not be included in the summary tables of AEs, unless otherwise stated.

Summary information (the number and percent of patients by system organ class (SOC) and PT separated by treatment group) will be tabulated for:

- All AEs (at patient level, and by event rate)
- All AEs causally related to durvalumab/placebo (as determined by the reporting investigator)
- AEs by maximum reported CTCAE grade
- AEs with CTCAE grade 3 or 4
- AEs with CTCAE grade 3 or 4, causally related to durvalumab/placebo (as determined by the reporting investigator)
- AEs with maximum CTCAE grade 3 or 4
- AEs with maximum CTCAE grade 3 or 4, causally related to durvalumab/placebo (as determined by the reporting investigator)
- Most common AEs
- AEs with outcome of death
- AEs with outcome of death causally related to durvalumab/placebo (as determined by the reporting investigator)
- All SAEs
- All SAEs causally related to durvalumab/placebo (as determined by the reporting investigator)
- AEs leading to discontinuation of durvalumab/placebo
- AEs leading to discontinuation of durvalumab/placebo, causally related to durvalumab/placebo (as determined by the reporting investigator)
- Other significant AEs
- Most common AEs with CTCAE grade 3 or higher
- AEs leading to dose delay of durvalumab/placebo

- AEs from start of first subsequent therapy until 90 days following discontinuation of study treatment
- AEs which started prior to first dose or after 90 days following date of last dose

An overall summary of the number and percentage of patients in each category will be presented. A truncated AE table of most common AEs and another table showing most common AEs with CTCAE grade 3 or 4, showing all events that occur in at least 5% of patients overall will be summarised by PT, by decreasing frequency in the total column (the total column will not be displayed in the AE tables). This cut-off may be modified after review of the data. When applying a cut-off (i.e., x %), the raw percentage should be compared to the cut-off, no rounding should be applied first (i.e., an AE with frequency of 4.9% will not appear if a cut-off is 5%). Summary statistics showing the time to onset and the duration of the first AE may also be presented as appropriate.

Each AE event rate (per 100 patient years) will also be summarised by PT within each SOC for the output summarising all AEs. For each PT, the event rate is defined as the number of patients with that AE divided by the total treatment duration (days) of randomised treatment summed over patients and then multiplied by 365.25 x 100 to present in terms of per 100 patient years.

Summaries of the number and percentage of patients with AEs will be provided by maximum reported CTCAE grade, SOC, PT and treatment group.

Fluctuations observed in CTCAE grades during study will be listed for those AEs which are CTCAE ≥ 3 .

In addition, all AEs will be listed.

Deaths

Two summaries of all deaths will be provided with number and percentage of patients by treatment group, categorised as:

- Total number of deaths (regardless of date of death)
- Death related to disease under investigation only as determined by the investigator
- Death related to disease under investigation and an AE with outcome of death

- AE onset prior to subsequent therapy. Which includes AEs with an onset date (or pre-treatment AEs that increase in severity) on or after the date of first dose and up to and including 90 days following the last dose of study medication

(durvalumab/placebo), or AE start date \leq the date of initiation of the first subsequent therapy (whichever occurs first).

- AE with outcome of death only
 - AE onset prior to subsequent therapy. Which includes AEs with an onset date (or pre-treatment AEs that increase in severity) on or after the date of first dose and up to and including 90 days following the last dose of study medication (durvalumab/placebo), or AE start date \leq the date of initiation of the first subsequent therapy (whichever occurs first).
- Death after end of safety follow up period (last dose of study medication (durvalumab/placebo) + 90 days) and not due to disease under investigation
- COVID-19 related death
- Unknown reason for death
- Other deaths

This summary will be repeated for all deaths on-treatment or within 90 days of last dose of durvalumab/placebo.

Adverse events of special interest and possible interest

Preferred terms used to identify adverse events of special interest and possible interest (as defined in [section 3.3.1](#)) will be listed before DBL and documented in the Study Master File. Grouped summary tables of certain MedDRA preferred terms will be produced and may also show the individual preferred terms which constitute each AESI/AEPI grouping. Groupings will be based on preferred terms provided by the medical team prior to DBL, and a listing of the preferred terms in each grouping will be provided.

An overall summary will include the number and percentage of patients with:

- Any AESI/AEPI (*)
- Any AESI/AEPI, causally related to durvalumab/placebo (*)
- Any AESI/AEPI of CTCAE grade 3 or 4
- Any AESI/AEPI of CTCAE grade 3 or 4, causally related to durvalumab/placebo
- Any AESI/AEPI with outcome of death
- Any AESI/AEPI with outcome of death, causally related to durvalumab/placebo

- Any serious AESI/AEPI (*)
- Any serious AESI/AEPI, causally related to durvalumab/placebo
- Any AESI/AEPI leading to discontinuation of durvalumab/placebo (*)
- Any AESI/AEPI leading to discontinuation of durvalumab/placebo, causally related to durvalumab/placebo
- Any AESI/AEPI leading to dose delay of durvalumab/placebo
- Any AESI/AEPI leading to concomitant medication (*)
- Any AESI/AEPI leading to concomitant medication use (steroids) (*)
- Any AESI/AEPI leading to concomitant medication use (high dose steroids) (*)
- Any AESI/AEPI leading to concomitant medication use (endocrine therapy) (*)
- Any AESI/AEPI leading to concomitant medication use (other immunosuppressants) (*)

Summaries of AESI/AEPI will also be produced, presenting the number and percentage of patients by group term and preferred term, in each of the selected categories above (*) and for patients with

- Any AESI/AEPI by maximum CTCAE grade
- Any AESI/AEPI causally related to durvalumab/placebo, by maximum CTCAE grade

AESI/AEPI will also be presented by outcome.

Another summary, presented by group term and type (AESI, AEPI, AESI or AEPI), will be tabulated presenting the number and percentage of patients with:

- Any AESI/AEPI
- Any serious AESI/AEPI
- Any AESI/AEPI of CTCAE grade 3 or 4
- Any AESI/AEPI causally related to durvalumab/placebo
- Any AESI/AEPI of CTCAE grade 3 or 4 causally related to durvalumab/placebo

- Any AESPI/AEPI leading to systemic corticosteroid use
- Any AESPI/AEPI leading to high dose steroid use
- Any AESPI/AEPI leading to use of other immunosuppressants
- Any AESI/AEPI leading to discontinuation of durvalumab/placebo
- Any AESI/AEPI with outcome of death
- Any AESI/AEPI not resolved
- Any AESI/AEPI resolved

A listing of AESI/AEPI will be provided, as well as a listing for those AESI/AEPI with outcome of death.

Immune-mediated Adverse events (imAEs)

The imAEs (as classified by the Sponsor) will be summarised in the similar manner as for the summaries for AESI/AEPI described above. See further details in the imAE Charter with respect to derivation rules.

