3.3 Safety variables

Safety and tolerability will be assessed in terms of AEs (including serious AEs [SAEs]), deaths, laboratory data, vital signs, electrocardiograms (ECGs) and exposure. These will be collected for all patients.

Unless otherwise specified, ‘on-treatment’ will be defined as assessments between date of the first dose and 90 days following last dose of the IP (durvalumab/placebo) or initiation of the first subsequent anti-cancer therapy (excluding palliative radiotherapy), whichever occurs first.

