3.3.5.1 Treatment exposure for durvalumab or placebo

If a patient has a delay to receiving study treatment, all tumour efficacy assessments and PRO assessments should still be conducted relative to the date of randomisation.

Total (or intended) exposure of durvalumab (MEDI4736) or placebo

- Total (or intended) exposure = min (last dose date where dose>0mg+27 days, date of death, date of DCO) – first dose date +1

Actual exposure of durvalumab (MEDI4736) or placebo

- Actual exposure = intended exposure – total duration of dose delays, where intended exposure will be calculated as above.

Calculation of duration of dose delays (for actual exposure):

- Since patients will receive 1500 mg via intravenous (IV) infusion q4w, the duration of dose delays will be calculated as follows:

For all dosing dates:

Total duration of dose delays= Sum of (Date of the dose - Date of previous dose – 28 days)

Thus, if no delays were encountered, the duration would sum up to 0, since infusions were done every four weeks.

Dose reductions are not permitted per the CSP for durvalumab. The actual exposure calculation makes no adjustment for any dose reductions that may have occurred.

Patients who permanently discontinue during a dose delay

If a decision is made to permanently discontinue study treatment in-between cycles or during a dose delay, then the date of last administration of study medication recorded will be used in the programming.

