4.2.12 Treatment exposure and intensity

The following summaries related to study treatment will be produced for the safety analysis set by treatment group:

- Total exposure
- Actual exposure (durvalumab or matching placebo only)

- Reasons for dose delays/interruptions. Dose interruptions will be based on investigator initiated dosing decisions
- Number of infusions received
- Relative dose intensity (RDI) (durvalumab or matching placebo only)
- Cumulative exposure over time

For patients on study treatment at the time of the IA, the DCO date will be used to calculate exposure.

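### The adverse event rate per 100 patient years divides first events by treatment time, not by time at risk, so its between-arm ratio can mislead

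*SAP*

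**What the plan says.** SAP 4.2.5.1 (Adverse events) promises: "Each AE event rate (per 100 patient years) will also be summarised by PT within each SOC for the output summarising all AEs". The rate for a PT is "the number of patients with that AE divided by the total treatment duration (days) of randomised treatment summed over patients", multiplied by 365.25 x 100.

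Three other passages decide what that fraction measures.

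- **Counting.** The same section states that "multiple events per patient will not be accounted", so a patient contributes at most one event per PT.
- **Event window.** The AE tables use "AEs observed up until 90 days following discontinuation of the study treatment (i.e., the last dose of randomised treatment) or until the initiation". The rest of that sentence names subsequent anti-cancer therapy (palliative radiotherapy excluded) as the alternative end point, and the earlier of the two applies. SAP 3.3 defines on-treatment the same way: "assessments between date of the first dose and 90 days following last dose of the IP (durvalumab/placebo"), again cut at subsequent therapy.
- **Treatment time.** Treatment duration is not defined under that name. The closest definition is total exposure in SAP 3.3.5.1, which ends at "min (last dose date where dose>0mg+27 days, date of death, date of DCO"). That section also defines actual exposure, which is shorter because dose delays are subtracted.

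Protocol 9.5.2 (Safety analyses) allows, as an option, AE rates per person-years at risk, and gives no formula.

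**The concern.** Readers will take a figure labelled per 100 patient years as adjusted for exposure and comparable between arms. Here the numerator and the denominator cover different time, in two ways.

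1. After a first event, a patient cannot add to the numerator for that PT but goes on adding days to the denominator. This lowers the rate, more so for common events and for longer treatment.
2. After the last dose, events count for up to 90 days but exposure for only 27. Up to 63 days per discontinued patient can add events without adding time. This raises the rate, more so in the arm treated for less time. If subsequent therapy starts within 27 days of the last dose, the mismatch reverses: days are counted in which events no longer are.

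Treatment continues until confirmed radiological progression unless another criterion stops it, so its length tends to follow efficacy and may differ between arms. Other things equal, the longer-treated arm looks safer than it is. If subsequent therapy starts sooner in the shorter-treated arm, the ratio for rare or moderately common events can instead exceed 1. Rates of common events are understated in both arms.

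**Working it through.** The plan states no AE rate, so there is no figure to reproduce. The check takes a case where the truth is known and asks what the SAP formula returns.

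**From the documents.** Events count to last dose + 90 days or subsequent therapy (SAP 4.2.5.1). The denominator runs to last dose + 27 days (SAP 3.3.5.1, total exposure). The window gap is 90 - 27 = 63 days. A month is 30.4375 days (SAP 4.1).

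**Assumed.** The hazard h is constant and equal in both arms (true ratio 1.0), at 5, 30 or 100 per 100 patient years. Time T to last dose is exponential, and follow-up is capped at c = 30 months = 913.1 days. The base case has medians of 8.6 v 5.6 months. The 3-month difference is the planned PFS benefit in Protocol 9.2, used as a stand-in for treatment time; the absolute medians are assumed.

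**Formulas.** Let m = median / ln 2, a = 1/m, and S = time from last dose to subsequent therapy (exponential with the stated mean, or none).

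- Window: W = min(T + min(90, S), c)
- Denominator: D = E[min(T + 27, c)] = 27 + m(1 - exp(-(c - 27)/m))
- Numerator: P = probability of an event by W. With no early subsequent therapy, P = 1 - exp(-90h) x a/(a + h) x [1 - exp(-(a + h)(c - 90))] - exp(-a(c - 90) - hc)
- SAP rate = P/D x 365.25 x 100

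**Base case.**

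- m = 8.6 x 30.4375/0.6931 = 377.6 days and 5.6 x 30.4375/0.6931 = 245.9 days.
- D = 27 + 377.6(1 - 0.096) = 368.5 days and 27 + 245.9(1 - 0.027) = 266.2 days.
- True 5: P = 0.0559 and 0.0434. Rates are 0.0559/368.5 x 36,525 = 5.5 and 0.0434/266.2 x 36,525 = 6.0. The ratio is 0.93.
- True 100: P = 0.611 and 0.532. Rates are 60.6 and 73.0. The ratio is 0.83.

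**Other cases.** Durvalumab:placebo ratio from the SAP formula, true ratio 1.0:

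| Median months on treatment (D v P) | Mean days to subsequent therapy (D v P) | True 5 | True 30 | True 100 |
|---|---|---|---|---|
| 8.6 v 5.6 | none early | 0.93 | 0.90 | 0.83 |
| 11 v 8 | none early | 0.96 | 0.93 | 0.89 |
| 5.6 v 8.6 | none early | 1.07 | 1.12 | 1.20 |
| 8.6 v 5.6 | 45 v 45 | 0.98 | 0.94 | 0.87 |
| 8.6 v 5.6 | 90 v 30 | 1.06 | 1.01 | 0.93 |
| 11 v 8 | 90 v 30 | 1.05 | 1.02 | 0.96 |
| 8.6 v 8.6 | 90 v 30 | 1.07 | 1.07 | 1.06 |
| 8.6 v 5.6 | 30 v 90 | 0.90 | 0.87 | 0.80 |

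A simulation of the same model agreed to within 0.01 in every row.

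**A wider gap.** A separate calculation used the median PFS of the earlier durvalumab trial (16.8 v 5.6 months, Protocol 2.3.1) as a proxy for treatment time, with no cap and no early therapy. With equal hazards of 5, 20, 50 and 100, the ratios are 0.81, 0.70, 0.58 and 0.48. A true 100 v 50 is reported as 35.7 v 46.6, a ratio of 0.77, so the direction reverses.

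**The at-risk denominator.** Replace D by E[min(event time, W)]. Under a constant hazard, P = h x E[min(event time, W)], so the rate equals h and the ratio is 1.00 in every row above.

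**Its limit.** With a hazard five times higher in the first 3 months (8.6 v 5.6, no early therapy), the at-risk ratios are 0.88, 0.89 and 0.93, against 0.82, 0.79 and 0.75 for the SAP formula. With therapy at 90 v 30 days as well, they are 0.85, 0.86 and 0.90, against 0.89, 0.86 and 0.79. For rare early-onset events the at-risk form is therefore not always nearer 1.

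**The case against.** The strongest reply is that the SAP states its formula openly and plans no rate ratio, interval or test. SAP 4.2.5 makes all safety summaries descriptive. Patients with the event per unit of exposure is a usable descriptive measure, and a clearer label would remove much of the risk of misreading. Exposure is tabulated by arm (SAP 4.2.12), some AE summaries ignore subsequent therapy, and time to onset may be shown. Every duration above is assumed, PFS is only a proxy for time on treatment, and the direction of the error is unknown. The 63-day gap also depends on reading treatment duration as total exposure.

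Most of this stands, and it limits the weight of the point. It does not remove it. The purpose of a rate per patient year is to adjust for unequal time, and this one does not do so reliably. Relabelling leaves events and time on different windows. The undefined term is part of the defect, and reading it as actual exposure would widen the gap. Because the protocol gives no formula, the SAP's departure from its person-years-at-risk description is an undeclared difference in definition, not a breach.

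A lighter remedy is to extend the common denominator to the AE window without stopping at first onset. In the constant-hazard cases this gives ratios of about 0.99 to 1.01 at a true 5, 0.95 to 1.05 at 30 and 0.87 to 1.13 at 100. It serves rare events well but not common ones.

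**Conclusion.** The concern holds and is minor. That the numerator and denominator cover different time follows from the SAP text alone. The size rests on assumed hazards, treatment times and therapy timing. In the constant-hazard table, a true ratio of 1.0 is reported as anything from 0.80 to 1.20. Equal treatment durations do not guarantee an undistorted ratio, as the 8.6 v 8.6 row shows. In the base case a true 100 per 100 patient years appears as about 61 and 73. The effect is confined to the all-AE rate by PT. The n (%) columns, all hypothesis tests and the alpha allocation are untouched.

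**What to change.** In SAP 4.2.5.1, define the rate for each PT as patients with the AE divided by summed time at risk in days, times 365.25 x 100. Time at risk runs from first dose to the earliest of:

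- first onset (or worsening) of that PT
- last dose + 90 days
- first subsequent anti-cancer therapy, excluding palliative radiotherapy
- death
- data cut-off

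This applies the on-treatment window of SAP 3.3 to both halves of the fraction. If system organ class rows also carry a rate, apply the same rule at that level. Add a footnote that the rate assumes a roughly constant hazard and still depends on treatment length for early-onset events.

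The cost is one sentence, one footnote and one derived denominator per PT, all from dates already collected. Reported rates will change in both arms and will no longer be n divided by a single exposure total.

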4.2.5.2 Laboratory assessments

Data obtained up until the 90 days following discontinuation of study treatment (durvalumab/placebo) or until the initiation of the first subsequent anti-cancer therapy (excluding palliative radiotherapy) following discontinuation of study treatment (whichever occurs first) will be used for reporting. This will more accurately depict laboratory toxicities attributable to study treatment only as some toxicities up to 90 days following discontinuation of the study treatment are likely to be attributable to subsequent therapy.

However, to assess the longer term toxicity profile, some summaries of laboratory data will be produced containing data collected up until 90 days following discontinuation of the study treatment (i.e., without taking subsequent therapy into account).

Any data post 90 days after the last dose of the study treatment will not be summarised.

Data summaries will be provided in preferred units.

Scatter plots (shift plots) of baseline to maximum value/minimum value (as appropriate) on-treatment may be produced for certain parameters if warranted after data review.

For continuous laboratory assessments, absolute value and change from baseline will be summarised using descriptive statistics at each scheduled assessment time by actual treatment group.

Shift tables for laboratory values by worst CTCAE grade will be produced, and for specific parameters separate shift tables indicating hyper- and hypo- directionality of change will be produced. The laboratory parameters for which CTCAE grade shift outputs will be produced are:

- Haematology: Haemoglobin; Leukocytes; Lymphocytes (count, absolute); Neutrophils (count, absolute); Platelets
- Clinical chemistry: alanine aminotransferase (ALT), aspartate aminotransferase (AST), alkaline phosphatase (ALP), Total Bilirubin, Albumin, Magnesium – low and – high, Sodium – low and – high, Potassium – low and – high, Corrected Calcium – low and – high, Glucose – low and – high, Creatinine, Lipase and Amylase.

Additional summaries will include a shift table for urinalysis (Bilirubin, Blood, Glucose, Ketones, Protein) comparing baseline value to maximum on-treatment value if a sufficient number of urinalysis assessments are recorded.

Haematology, clinical chemistry and urinalysis laboratory data will be listed.

Liver enzyme elevations and Hy's law

A summary will include the number (%) of patients who have:

- Elevated ALT, AST, and Total bilirubin during the study
 - ALT $\geq 3x$ – $\leq 5x$, $> 5x$ – $\leq 8x$, $> 8x$ – $\leq 10x$, $> 10x$ – $\leq 20x$, and $> 20x$ upper limit of normal (ULN) during the study
 - AST $\geq 3x$ – $\leq 5x$, $> 5x$ – $\leq 8x$, $> 8x$ – $\leq 10x$, $> 10x$ – $\leq 20x$, and $> 20x$ ULN during the study
 - Total bilirubin $\geq 2x$ – $\leq 3x$, $> 3x$ – $\leq 5x$, $> 5x$ ULN during the study
 - ALT or AST $\geq 3x$ – $\leq 5x$, $> 5x$ – $\leq 8x$, $> 8x$ – $\leq 10x$, $> 10x$ – $\leq 20x$, $> 20x$ ULN during the study.
 - ALT or AST $\geq 3x$ ULN and Total bilirubin $\geq 2x$ ULN during the study (Potential Hy's law): The onset date of ALT or AST elevation should be prior to or on the date of Total Bilirubin elevation

This summary will be repeated based on laboratory assessments with a date ≤ 90 days after last dose.

Liver biochemistry test results over time for patients with elevated ALT or AST (i.e. $\geq 3x$ ULN), and elevated Total Bilirubin (i.e. $\geq 2x$ ULN) will be plotted (the onset date of ALT or AST elevation should be prior to or on the date of Total Bilirubin elevation). Individual patient data where ALT or AST (i.e. $\geq 3x$ ULN) plus Total Bilirubin (i.e. $\geq 2x$ ULN) are elevated will be listed also (the onset date of ALT or AST elevation should be prior to or on the date of Total Bilirubin elevation).

Plots of ALT and AST vs. Total Bilirubin by treatment group will also be produced with reference lines at $3 \times ULN$ for ALT, AST, and $2 \times ULN$ for Total Bilirubin. In each plot, Total Bilirubin will be on the vertical axis.

Liver diagnostic investigations, risk factors and lifestyle events as well as liver signs and symptoms will be listed.

Assessment of Thyroid Function Test Results

The following summaries will include the number and percentage of patients who have elevated or low TSH.

- On-treatment elevated TSH $> ULN$
- On-treatment elevated TSH $> ULN$ with TSH $\leq ULN$ at baseline
- On-treatment elevated TSH $> 3 \times ULN$
- On-treatment elevated TSH $> 3 \times ULN$ with TSH $\leq ULN$ at baseline
- On-treatment elevated TSH $> 10 \times ULN$
- On-treatment elevated TSH $> 10 \times ULN$ with TSH $\leq ULN$ at baseline;
- On-treatment low TSH $< LLN$
- On-treatment low TSH $< LLN$ with TSH $\geq LLN$ at baseline

A separate summary will present:

- Number of patients with at least one baseline and post-baseline TSH result
 - o On-treatment elevated TSH $> ULN$ and above baseline
 - o On-treatment decreased TSH $< LLN$ and below baseline

Thyroid function test laboratory data will be listed.

Assessment of Renal Function Test Abnormalities

In addition to the analysis for serum creatinine, the number and percentage of patients with CrCl rate during treatment period meeting the following categories will be presented:

- Normal: CrCl \geq 90 mL/min
- Mild Impairment: CrCl \geq 60 - < 90 mL/min
- Moderate Impairment: CrCl \geq 30 - < 60 mL/min
- Severe Impairment: CrCl \geq 15 - < 30 mL/min
- Kidney Failure: CrCl < 15 mL/min

A summary of the reversibility of CrCl will be provided as the number and percentage of patients who shifted to a worse on-treatment renal impairment category from baseline and the number and percentage of patients whose worsened renal impairment was reversible and transient, defined as subsequent CrCl value that is higher than the worst on-treatment CrCl value and in a better impairment category.

CrCl rate will be calculated using serum Creatinine and the Cockcroft-Gault formula ([Cockcroft and Gault 1976](#)).

